8.0 STUDY EFFICACY AND SAFETY ASSESSMENTS

8.1 Efficacy Assessments

Patients will initially be flagged as potential candidates for the trial following a local tumor board discussion that the location and overall clinical picture would allow for either treatment as a viable option. Once tumor board agreement has been obtained, patients will be scheduled for a multi- disciplinary clinic visit where they will have a complete clinic visit with interventional radiology and radiation oncology back-

to-back. If after these visits patients fulfill inclusion/exclusion criteria, they will immediately thereafter be approached by a research coordinator and enrollment will be attempted.

If patients decline participation, a detailed screen fail form will be filled out to try and best ascertain reasons for declined participation. If the patient agrees to participate, they will be enrolled and randomized (as described above) at that time.

A virtual/telehealth provision will be permitted for all follow-up visits. Since the virtual visit does not allow for effective physical exam of all body systems and vitals are unable to be obtained virtually, these elements will not be required during virtual visits. Labs will be obtained, however, as well as required imaging. If questionnaires are required during a virtual/telehealth visit, they may be administered via REDCap survey.

Baseline: Labs, medical history/physical exam and PROs questionnaires will be obtained during the initial clinic visit prior to randomization. Subjects will be required to have an MRI or CT of the abdomen within 3 months of enrollment.

Pre-Treatment: Patients will return for functional hepatobiliary scan and treatment planning procedures prior to treatment (≤ 30 days from enrollment)

Treatment: Patients will undergo treatment as described above in Section 7.1.

Follow Up Visits:

One month (± 15 days) after treatment completion patients will return for a clinic visit with labs (CBC, CMP, INR, AFP (if elevated at baseline)), physical exam, and PROs using FACT-G and COSTFACIT.

Three months after treatment completion (± 30 days) patients will return for a clinic visit with labs (CBC, CMP, INR, AFP (if elevated at baseline)), physical exam, and PROs using FACT-G and COST FACIT. Patients will also undergo multi-phase contrast enhanced CT or MR of the abdomen and functional hepatobiliary scan.

Six months after treatment completion (± 30 days) patients will return for a clinic visit with labs (CBC, CMP, INR, AFP (if elevated at baseline)), physical exam, and PROs using COST FACIT and FACT-G. Patients will also undergo multi-phase contrast enhanced CT or MR of the abdomen and ORR will be measured by two separate abdominal radiologists, using mRECIST, who will have been blinded to the treatment received.

9-24 months: Patients will continue to be followed every three months in clinic with labs, physical exam, and imaging per standard of care. Further intervention will be performed (if needed) as standard of care and DFS and TTST will be recorded up to 2 years from the completion of treatment.

8.2 Safety and Other Assessments

Both treatment arms are currently being performed as standard of care. The PI will ultimately monitor safety with direct monitoring for AEs collected by research personnel with discussion with the PI as needed. Comparison of toxicities (≥ grade 4) will be performed as a secondary endpoint. The most common expected toxicities are fatigue and liver toxicity.

9.0 PARTICIPANT DISCONTINUATION/WITHDRAWAL

Participants may withdraw voluntarily from the study, the PI may discontinue a participant from the study, or patients may be lost to follow-up. The overall estimation of total unanalyzable accruals is 10%.

9.1 Study Intervention Not or Incompletely Performed

Study intervention arms both include a single treatment of the tumor, rather than an ongoing treatment. There is essentially one foreseeable area for necessary discontinuance in each arm.

Patients in the RS arm could potentially be found to have arterial anatomy precluding RS (3 or more segmental arteries supplying tumor or high lung shunt). While this is felt unlikely, it would preclude them from RS and they will be unanalyzable and removed from study to receive off-protocol treatment.

Patients in the SBRT arm will be monitored weekly for toxicities while on-treatment. While it is unexpected for patients to demonstrate toxicities that would preclude completion of the therapy cycle, if this were to occur, patients would be evaluated in the SBRT treatment arm, but designated to have had incomplete treatment.

9.2 Participant Discontinuation/Withdrawal from the Study

Participants are free to withdraw from participation in the study at any time upon request. An investigator may discontinue or withdraw a participant from the study for the following reasons:

- 1. Pregnancy
- 2. Significant study intervention non-compliance
- 3. If any clinical adverse event (AE), laboratory abnormality, or other medical condition or situation occurs such that continued participation in the study would not be in the best interest of the participant
- 4. The study is terminated (see section 12.1.2)

The reason for participant discontinuation or withdrawal from the study will be recorded on the Case Report Form (CRF).

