13.1.2 Definition of Serious Adverse Events (SAE)

A serious adverse event is any untoward medical occurrence resulting in one or more of the following:

- 1. Results in death or ANY death occurring within 30 days of treatment
- 2. Is life-threatening (defined as an event in which the patient was at risk of death at the time of the event; it does not refer to an event which hypothetically might have caused death if it were more severe)
- 3. Requires inpatient hospitalization \geq 24 hours or prolongation of existing hospitalization

NOTE: Hospitalizations that are not considered SAEs are:

- Hospitalization planned prior to biopsy procedure
- Hospitalization < 24 hours in duration
- Hospitalization for elective treatment of a pre-existing condition unrelated to biopsy procedure.
- 4. Results in persistent or significant disability/incapacity
- 5. Is a congenital anomaly or birth defect
- 6. Is an important medical event (defined as a medical event(s) that may not be immediately life-threatening or result in death or hospitalization but, based upon appropriate medical and scientific judgment, may jeopardize the patient or may require intervention (e.g., medical, surgical) to prevent one of the other serious outcomes listed in the definition above). Examples of such events include, but are not limited to, intensive treatment in an emergency room or at home for allergic bronchospasm; blood dyscrasias or convulsions not resulting in hospitalization; or the development of drug dependency or drug abuse.

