13.4 REPORTING ADVERSE EVENTS

Adverse events will be recorded from the time of informed consent and for 30 days after the 6 month visit regardless of whether or not the event(s) are considered related to the study procedure. All AEs considered related to study procedures will be followed until resolution, return to baseline, or deemed clinically insignificant, even if this is after the 6 month visit Any death occurring within 30 days after intervention must be reported as an SAE regardless of attribution.

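### Section 9.2 allows withdrawal from the whole study rather than from the intervention alone, so follow-up data may be lost in a way related to toxicity

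*Combined protocol and SAP*

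**What the plan says.** Section 9.2 opens its list with "An investigator may discontinue or withdraw a participant from the study for the following reasons". Apart from termination of the study itself, the grounds are pregnancy, "Significant study intervention non-compliance", and a medical ground that begins "If any clinical adverse event (AE), laboratory abnormality, or other medical condition or situation occurs such that continued participation in the study". The limiting condition on that last ground is that the event "occurs such that continued participation in the study would not be in the best interest of the participant". The only data item 9.2 asks for at withdrawal is the reason, on the case report form.

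Section 9.1 describes the treatment differently from a continuing drug: "Study intervention arms both include a single treatment of the tumor, rather than an ongoing treatment". For SBRT patients whose toxicity prevents completion, it says that "patients would be evaluated in the SBRT treatment arm, but designated to have had incomplete treatment".

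On safety data, 13.4 states: "Adverse events will be recorded from the time of informed consent and for 30 days after the 6 month visit". Section 13.3 sets the tail at 7 days for non-serious and 30 days for serious events after the same visit. It also requires that recorded events be followed to resolution and that changes in their severity be documented. Section 13.4 extends follow-up of related events beyond the 6-month visit where needed.

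Section 10.4 specifies a modified intention-to-treat analysis. It names one exclusion: patients randomised to RS and found ineligible at the planning arteriogram.

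**The concern.** Where treatment continues, withdrawing a patient for an adverse event removes a possible cause of harm. Here, once the RS administration or the SBRT fractions have been given, what is left of participation is visits, labs, imaging, a second HIDA scan and questionnaires. Withdrawal from the study at that stage takes away observation and no study treatment.

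Two of the grounds, the medical one and non-compliance with the intervention, can follow from toxicity. Dropout could then depend on the outcome that secondary objective 1 compares (toxicity of grade 4 or higher). It could also affect the HIDA, questionnaire, ORR, DFS and TTST results. Opportunities to trigger withdrawal may differ by arm: SBRT patients are seen with labs at least weekly during treatment (7.1.2), while RS is a single administration.

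**Working it through.** The plan has no computed figure on this point to reproduce, so the check is a comparison of texts plus simple counts.

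1. **Scope.** 9.2 speaks of leaving the study. Neither 9.1 nor 9.2 defines a state in which the intervention has stopped but follow-up continues, except the SBRT sentence in 9.1.

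2. **What survives withdrawal.** 13.3 and 13.4 contain no exemption for withdrawn patients. An event recorded before withdrawal is therefore still followed, and a rise in its grade should still be documented.

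3. **What has no provision.** No section says that scheduled assessments or enquiry about new events continue after a 9.2 withdrawal. The Schedule of Events has 9 post-treatment visits (months 1, 3, 6, 9, 12, 15, 18, 21, 24). For a participant withdrawn just after the 1-month visit:
   - visits not reached: 9 − 1 = 8;
   - follow-up imaging not reached: all 8 time points (months 3 to 24), including the 6-month ORR scan;
   - the 3-month HIDA scan, and the month 3 and 6 labs and questionnaires, not obtained;
   - DFS and TTST observation not obtained: up to 24 − 1 = 23 months.

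4. **End of adverse-event recording.** The 6-month visit falls at 180 ± 30 days from the end of treatment, that is, days 150 to 210. Adding the 30 days of 13.4 gives an end between days 180 and 240. With the 7 days of 13.3 for non-serious events it is days 157 to 217. A participant without a 6-month visit has no such anchor. Section 4.2 does count the toxicity endpoint itself from treatment, up to 6 months. The gap is therefore in the collection rule and not in the endpoint definition.

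5. **9.1 against 9.2.** Take one SBRT patient who stops early for toxicity. Under 9.1 the patient is evaluated in the SBRT arm and flagged as incompletely treated. Under 9.2 the same patient may be withdrawn, either on the medical ground or possibly as non-compliant. No order of precedence is given. The two can be read together, so this is a tension and not a flat contradiction.

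6. **Analysis.** Neither 10.4 nor 10.5 says how patients withdrawn under 9.2 enter the Fisher tests, t-tests or Kaplan-Meier estimates.

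7. **Scale.** With 10 per arm, one patient is 1/10 = 10% of an arm. The 10% allowance for unanalysable accruals in 9.0 is 0.10 × 20 = 2 patients, from all causes.

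**The case against.** The strongest reply is that 9.2 is permissive and conditional: the medical ground applies only where staying in would be against the participant's interest, and few investigators would use it merely to stop watching a patient. Withdrawal can also occur before treatment, or between SBRT fractions. Even afterwards it can spare a participant something, since 2.3 names the HIDA scan as an added risk for RS patients beyond standard care, and it is repeated at 3 months. All of this stands. It limits how often the problem will arise and shapes the remedy, but it does not supply the missing distinction.

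A reader might infer more than the documents support:

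- **That safety follow-up is lost.** 13.3 and 13.4 still cover recorded events, and 13.3 allows events to be found on review of the medical record. The exposure is limited to new events and scheduled assessments.
- **That a toxicity rate would shift by a stated amount**, for example from 2/10 to 0/8 if both patients in the 10% allowance were toxicity withdrawals in one arm. This assumes that their events go uncounted and that they leave the denominator. 10.4 says neither, and the allowance also includes RS patients with unsuitable anatomy. Even so, against 0/10 in the other arm the Fisher p-value would be 0.47 for 2/10 and 1.00 for 0/8, so neither comparison would be informative.
- **That 9.2 contradicts 13.1.2**, where one criterion reads "Is a congenital anomaly or birth defect". That section defines a serious event and sets no duty of follow-up, so there is nothing for 9.2 to contradict.
- **That fetal exposure would go unrecorded.** Pregnancy as the reason for withdrawal must be entered on the case report form.

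**Conclusion.** The point holds in a limited form. 9.2 leaves open a route to outcome-related loss of secondary data, and for SBRT patients who stop early it offers a different fate from the one in 9.1. The conclusion assumes that withdrawal from the study means what it says, an end to scheduled study assessments, and that the discretion is used for at least one participant after treatment. The direction and size of any bias cannot be derived from the documents.

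The primary endpoint, recruitment at 6 and 12 months and screen failures when patients are approached, is fixed before any such withdrawal and is not affected. The comparisons at risk are secondary, in arms of 10, with no power claimed. This is a worthwhile, inexpensive improvement and does not threaten the trial's main purpose.

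**What to change.** Amend the wording in three places:

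- **9.2 (with 9.1).** Make discontinuing the intervention distinct from leaving the study. State that participants remain in the already scheduled follow-up and adverse-event collection unless they withdraw consent, and that individual assessments may be omitted where the investigator judges them unsuitable. Say which text governs SBRT patients who stop early. The grounds for stopping treatment need not change, and this review proposes none.
- **13.3 and 13.4.** For participants with no 6-month visit, give adverse-event collection an end date counted from the end of treatment, or from randomisation if untreated. Reconcile the 7-day and 30-day tails for non-serious events at the same time.
- **10.4.** State that, apart from the RS-ineligible patients already excluded, participants withdrawn under 9.2 are analysed in their randomised arm with data to last contact.

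As housekeeping, 9.2 points to section 12.1.2 for study termination. That section does not exist in the current text, and the material is in 12.2.

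The cost is an amendment and a little more tracking. No visits are added to the schedule, and 8.1 already permits virtual follow-up visits, with labs and required imaging still obtained.

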9.3 Lost to Follow-Up

A participant will be considered lost to follow-up if he or she fails to return for 2 sequential scheduled visits and is unable to be contacted by the study site staff.

10.0 STATISTICAL CONSIDERATIONS

10.1 Executive Summary

The proposed study is a randomized pilot study evaluating feasibility as measured by screen failures and recruitment rate into a randomized trial comparing RS and SBRT. Secondary objectives will involve comparison of toxicities, effect on liver function, effect on patient reported outcomes and measurement of ORR of RS and SBRT to better allow for an appropriately powered trial evaluating the efficacy of these treatments. DFS and TTST will also be measured up to 2 years after completion of initial treatment.

10.2 Statistical Analysis

10.2.1 Primary Objectives/Endpoints

1. Primary Endpoint: Recruitment rates measured at 6 and 12 months and screen failures assessed by the detailed screen failure form at the time patients are approached for enrollment to ascertain specific reasons why patients may choose not to enroll

Primary Objective: To assess feasibility as measured by screen failures and rate of recruitment into a randomized trial comparing RS and SBRT for patients with small (≤3 cm) solitary hepatocellular carcinoma (HCC).

10.2.2 Secondary Objectives/Endpoints

1. SE: Laboratory (CBC, CMP, INR)/clinical toxicities measured using CTCAE version 5.0

SO: To compare the proportion of any toxicities (\geq grade 4) using CTCAE version 5.0 between RS and SBRT for patients with small (\leq 3 cm) solitary hepatocellular carcinoma (HCC) up to 6 months after treatment.

NH: The proportion of any toxicities (\geq grade 4), using CTCAE version 5.0, between RS and SBRT for patients with small (\leq 3 cm) solitary hepatocellular carcinoma (HCC) are equal.

AH: The proportion of any toxicities (\geq grade 4), using CTCAE version 5.0, between RS and SBRT for patients with small (\leq 3 cm) solitary hepatocellular carcinoma (HCC) are not equal.

2. **SE:** Change in % radiotracer extraction from baseline, on functional HIDA scan, 3 months after treatment

SO: To compare the mean change in hepatobiliary function, as measured 3 months after treatment using a functional HIDA scan, between RS and SBRT for patients with small (≤3 cm) solitary hepatocellular carcinoma (HCC).

NH: The mean change in hepatobiliary function, as measured 3 months after treatment using a functional HIDA scan, will be equal between RS and SBRT for patients with small (≤3 cm) solitary hepatocellular carcinoma (HCC).

AH: The mean change in hepatobiliary function, as measured 3 months after treatment using a functional HIDA scan, will not be equal between RS and SBRT for patients with small (≤3 cm) solitary hepatocellular carcinoma (HCC).

3. **SE:** Change in FACT-G and COST FACIT from baseline at 3 and 6 months

SO: To compare the mean change in patient-reported outcomes from baseline, at 3 and 6 months, between RS and SBRT, for patients with small (≤3 cm) solitary hepatocellular carcinoma (HCC), using FACT-G and COST FACIT.

NH: The mean change in patient-reported outcomes from baseline, at 1, 3 and 6 months, will be equal between RS and SBRT, for patients with small (≤3 cm) solitary hepatocellular carcinoma (HCC), using FACT-G and COST FACIT.

AH: The mean change in patient-reported outcomes from baseline, at 1, 3 and 6 months, will not be equal between RS and SBRT, for patients with small (≤3 cm) solitary hepatocellular carcinoma (HCC), using FACT-G and COST FACIT.

4. SE: DFS at 2 years after treatment completion as measured with mRECIST on CT or MR

SO: To compare the disease-free survival (DFS) rates of RS and SBRT at 2 years using mRECIST on CT or MR for patients with small (\leq 3 cm) solitary hepatocellular carcinoma (HCC).

NH: The disease-free survival (DFS) rates will be equal between RS and SBRT at 2 years using mRECIST on CT or MR for patients with small (\leq 3 cm) solitary hepatocellular carcinoma (HCC).

AH: The disease-free survival (DFS) rates will not be equal between RS and SBRT at 2 years using mRECIST on CT or MR for patients with small (≤3 cm) solitary hepatocellular carcinoma (HCC).

5. **SE:** TTST for target tumor up to 2 years following treatment.

SO: To compare time-to-secondary treatment (TTST) between RS and SBRT for patients with small (≤3 cm) solitary hepatocellular carcinoma (HCC) up to 2 years after initial treatment.

NH: The time-to-secondary treatment (TTST) between RS and SBRT for patients with small (≤3 cm) solitary hepatocellular carcinoma (HCC) up to 2 years after initial treatment will be equal.

AH: The time-to-secondary treatment (TTST) between RS and SBRT for patients with small (≤3 cm) solitary hepatocellular carcinoma (HCC) up to 2 years after initial treatment will not be equal.

6. **SE:** ORR at 6 months after completion of treatment using mRECIST on multiphase CT or MR.

SO: To evaluate the objective response rate (ORR) of radiation segmentectomy (RS) and stereotactic body radiation therapy (SBRT) as measured at 6 months using mRECIST for patients with small (\leq 3 cm) solitary hepatocellular carcinoma (HCC).

NH: The objective response rates (ORR) of radiation segmentectomy (RS) and stereotactic body radiation therapy (SBRT) are equal, as measured at 6 months using mRECIST for patients with small (\leq 3 cm) solitary hepatocellular carcinoma (HCC).

AH: The objective response rates (ORR) of radiation segmentectomy (RS) and stereotactic body radiation therapy (SBRT) are not equal, as measured at 6 months using mRECIST for patients with small (\leq 3 cm) solitary hepatocellular carcinoma (HCC).

10.3 Sample Size Projections

The primary objective of the pilot study will be to access feasibility. 20 patients in total will be enrolled, with up to 10 patients per arm (depending on the amount of screen fails). These numbers should be sufficient for the assessment of feasibility.

10.4 Populations for Analyses

The study will be performed as a modified Intention-to-treat analysis. Patients who were randomized to the radiation segmentectomy arm, but were later found to be to ineligible for RS based on the planning arteriogram findings, will be considered unanalyzable as they will have not received any protocol therapy and will proceed to other standard of care therapy. If this were to occur, a replacement patient will be added into the RS arm to help ensure a total of 10 patients in each arm.

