7.2 Measures to Minimize Bias: Randomization and Blinding

Patients enrolling in trial will undergo permuted block randomization in groups of 4 at the time of enrollment. This will happen at the time of randomization using simple randomized opaque envelopes. Overall blinding is not feasible for this trial given that each arm features a different therapy administered in different departments of the hospital. Given that the primary endpoint is ORR at 6 months, a diagnostic radiologist reviewing for response (and DFS) will be blinded to the therapyarm.

7.3 **Concomitant Therapy**

No active systemic therapy for the treatment of HCC will be allowed from the time of enrollment to the time of primary outcome assessment. Expected supportive medication generally given as standard of care with either therapy arm will be allowed.

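### Section 10.4 puts the replacement for an RS mapping failure straight into the RS arm, which as written implies non-random assignment and conflicts with Sections 7.2 and 8.1

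*Combined protocol and SAP*

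**What the plan says.** Section 10.4 defines a modified intention-to-treat analysis. Patients randomised to RS who are ruled out by the planning arteriogram "will be considered unanalyzable as they will have not received any protocol therapy and will proceed to other standard of care therapy". The section then provides that "a replacement patient will be added into the RS arm to help ensure a total of 10 patients in each arm". It does not say how the replacement is allocated, what that patient is told at consent, or whether that patient counts towards recruitment.

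Section 7.2 states the allocation rule: "Patients enrolling in trial will undergo permuted block randomization in groups of 4 at the time of enrollment". On the mechanism it adds: "This will happen at the time of randomization using simple randomized opaque envelopes". Section 8.1 says that a patient who agrees to take part is enrolled and randomised on the spot. Neither section makes an exception for replacements.

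On size, Section 10.3 says "20 patients in total will be enrolled" and sets a ceiling of 10 per arm; the Synopsis agrees. Section 9.1 repeats the removal of RS mapping failures. It has no replacement rule for stereotactic body radiation therapy (SBRT): if SBRT is not completed, "patients would be evaluated in the SBRT treatment arm, but designated to have had incomplete treatment".

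**The concern.** Naming the replacement's arm in advance departs from the one feature that makes the two groups comparable. Treatment is open, and under Section 5.3 a coordinator or investigator approaches patients after both clinic visits. Staff who know that the open place is RS could, even unintentionally, choose whom to approach for it. Concealed envelopes exist to prevent that.

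The patient so placed would then enter every between-arm comparison in Section 10.5.3: toxicity, HIDA change, patient-reported outcomes, disease-free survival, time to secondary treatment and response. The rule works on one arm only.

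There is also a possible effect on the primary endpoint. The pilot asks whether patients will accept randomisation, and the screen fail form in Appendix VI lists preference for one treatment among its refusal reasons. A patient offered a certain RS place would not face that decision.

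**Working it through.** **1. The plan's own figure.** The inputs are 20 patients (Section 10.3) and blocks of 4 (Section 7.2). 20 / 4 = 5 complete blocks, and with 2 places per arm in each block this gives 5 × 2 = 10 per arm. The stated 10 + 10 reproduces exactly, so the planned list holds no spare RS place.

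**2. Can the replacement be randomised and still be sure to enter RS?** Suppose the 20 envelopes are used and a fresh 2:2 block of 4 is opened. The first RS place comes at:
- position 1 with probability 2/4 = 1/2
- position 2 with probability (2/4)(2/3) = 1/3
- position 3 with probability (2/4)(1/3) = 1/6

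The mean is 1 × 1/2 + 2 × 1/3 + 3 × 1/6 = 1.67 enrolments, with a maximum of 3. With probability 1/3 + 1/6 = 1/2, at least one extra SBRT patient is enrolled first, which takes SBRT above the ceiling of 10. Random replacement therefore cannot guarantee what Section 10.4 aims for within the limits of Section 10.3. Direct assignment can.

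**3. How many patients are affected?** Section 9.1 calls mapping failure unlikely and gives no rate, so the rate f is assumed. Among 10 RS patients, the expected number of failures is 10f and the chance of at least one is 1 − (1 − f)^10.

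| Assumed f | Expected failures | Chance of at least one |
|---|---|---|
| 5% | 0.5 | 40% |
| 10% | 1.0 | 65% |
| 20% | 2.0 | 89% |

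Each replacement is 1/10 = 10% of the RS arm. As a check on the range, Section 9.0 expects 10% of all accruals to be unanalysable, that is 20 × 0.10 = 2 patients for all causes and both arms. The top of the assumed range would spend that whole allowance on RS mapping failure.

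**4. Effect on measured recruitment.** The plan does not define the rate. Take as denominator, by assumption, the 50 to 60 eligible patients a year in Section 5.3. Without replacements the rate is 20/60 = 33.3% to 20/50 = 40.0%. With one replacement counted on top of the 20, it is 21/60 = 35.0% to 21/50 = 42.0%. The shift is 1.7 to 2.0 points. The exact 95% intervals are 21.7% to 46.7% for 20/60 and 26.4% to 54.8% for 20/50, so one patient moves the estimate by far less than its sampling error.

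**The case against.** The strongest reply is that Section 10.4 concerns analysis populations, not allocation. It says which arm is to be topped up, in soft terms, while Sections 7.2 and 8.1 govern how patients enter and allow no exception. On that view the text is incomplete rather than wrong. This stands to the extent that the plan never expressly says the replacement is unrandomised. It does not remove the conflict: the sentence fixes the arm in advance, and step 2 above shows that randomisation cannot guarantee that result.

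Three stronger inferences are tempting, and the documents do not support them.
- *The replacement consents to a known treatment.* The plan does not describe consent for replacements; this follows only if assignment is direct and disclosed.
- *Recruitment is inflated.* That would require the replacement to be counted and to be someone who would have refused randomisation. Neither is established. If the mapping failure is dropped from the count and the replacement takes that place, the count stays at 20.
- *Replacements come late and so differ in calendar time.* Pre-treatment procedures fall within 30 days of enrolment (Sections 1.3 and 8.1), so a failure can surface and be replaced at any point in the estimated 12 months of accrual.

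It is also fair to say that going beyond 20 is no argument against direct assignment in particular, since randomised replacement does so too. Finally, this is a feasibility pilot with no power calculation, and about one patient is at issue. That limits the size of the problem, but the remedy is cheap.

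**Conclusion.** The point holds as a conflict over allocation. Followed as written, Section 10.4 would put non-randomised patients into the RS arm and into every between-arm secondary comparison, contrary to Sections 7.2 and 8.1. The likely size is about one patient: 0.5 to 2 expected under the assumed 5% to 20% failure rate, with the upper end hard to square with the plan's own allowance for unanalysable accruals. The effect on the primary endpoint is only possible, and small. It depends on an undefined rate, on the replacement being counted, and on the assumed pool of 50 to 60. The plan should be changed before a replacement is needed, because a directly assigned patient cannot be made a randomised one afterwards.

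**What to change.** In Section 10.4, substitute for the replacement sentence: *Any replacement is randomised using the next unused concealed envelope from an extended permuted-block list; unequal final arm sizes are accepted.* Three matching changes are needed.

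- Amend the Synopsis and Section 10.3 so that the total of 20 and the ceiling of 10 per arm allow for replacements.
- State in Section 10.5.2 that mapping failures stay in the recruitment count, since they did accept randomisation, and that replacements are shown separately.
- Prepare spare concealed envelopes beyond the first 20.

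If direct assignment is really intended, the plan should say so, and those patients should be left out of the recruitment rate and the randomised comparisons.

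The cost is a few sentences and envelopes. With one replacement for one failure, drawn from a fresh block, 21 patients are enrolled and the analysable arms finish 10 v 10 or (RS v SBRT) 9 v 11 with equal probability. If the team instead insists on filling the RS place, it takes 1.67 enrolments on average and at most 3, against 1 under direct assignment, provided the new RS patients do not themselves fail mapping.
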